1.2 Rationale

The rationale for this study is based on several premises:

- The need to understand the immunological, viral and host factors related to the resistance to HIV-1 acquisition, by high-risk individuals, for the design and evaluation of HIV-1 prevention strategies for the HPTN.
- The unique opportunity to investigate the immunological, viral and host factors related to resistance to HIV-1 infection in Pune.
- The opportunity, through this laboratory protocol, to assess the feasibility of identifying, enrolling and retaining exposed partners and their highly infectious partners with recent HIV-1 infection, in a unique prospective cohort of discordant couples for future HPTN clinical trials.

The overall aim of this study is to investigate the immunologic, virologic and genetic factors that impact upon acquisition of or protection from HIV-1 infection. These studies would provide data that would be critical for designing prevention strategies involving the use of antiretrovirals, microbicides and vaccines.

An equally important goal of this study is to begin to transfer the technology of virologic and immunologic assays to the NARI HPTU, so that these measurements can be made on-site, instead of being shipped to and performed at a central location. Currently, novel immunologic assays, such as the ELISPOT and a flow cytometric assay for measuring intracellular cytokine levels are being developed and standardized for use on-site in large, multi-site clinical trials. The HPTN Central Laboratory (HCL) will coordinate the development of consensus protocols and transfer of the technology for immunologic assays to NARI. This proposal will be coordinated with the 034A HPTN Early Infection Laboratory Sub-study. The first step in performing these kinds of tests in a consistent, standardized way is to establish a well- organized, accessible repository of PBMC and plasma samples on-site. The goal of this protocol is to outline procedures to create such a repository for future studies to be carried out on-site when consensus protocols have been developed and implemented. This sub-study will also develop quality control measures to assure consistent sample collection and processing at the NARI HPTU site in preparation of future studies to be developed by the HPTN.

The HPTN will encompass the largest network to date of cohorts of acutely infected individuals and their uninfected partners from countries around the world that continue to have a significant incident of HIV-1 infection. These cohorts will allow for the characterization of distinct viral subtypes and of the immune response to these different subtypes of HIV-1 in individuals with genetically diverse backgrounds (eg HLA, co-receptor genotype, etc), as well as a variety of factors that may impact the primary immune response to HIV-1 (eg. micronutrient deficiency, co-infections, viral load). Understanding the significance of viral characteristics and mechanisms and their relationship to potential immune correlates of protection for HIV-1, such as CTL recognition, is a primary goal of the HPTN. In addition, this protocol would provide standardization of specimen collection for additional HPTN protocol specific studies in the future.

2.0 STUDY OBJECTIVES AND DESIGN

2.1 Primary Objectives

- To determine if the detection of an HIV-1 -specific immune response in exposed uninfected individuals correlates with risk of subsequent HIV-1 infection.
- To determine if immunologic genetic characteristics of exposed uninfected individuals correlates with risk of subsequent HIV-1 infection.

2.2 Secondary Objectives:

- To determine if the detection of an HIV-1 -specific immune response in exposed uninfected individuals correlates with the HIV-1 viral set point in individuals that subsequently become HIV-1 infected.
- To compare the epitope specificity of the HIV-1 -specific immune response of exposed-uninfected individuals with that of their recently infected partners.
- To assess the feasibility of establishing a prospective cohort of recently infected individuals and their primary sexual partners for participation in HPTN HIV-1 prevention trials of discordant couples.

2.3 Study Design:

This is a prospective cohort study to be conducted at NARI. NARI will implement the study in accordance with this protocol, however additional studies and collaborations may be incorporated into this study with approval from the Executive Committee. NARI will document study data using standard data collection forms to be submitted to the HPTN Statistical and Data Management Center (SDMC).

An estimated 10-15 individuals/year who qualify as HIV-1 -exposed uninfected are expected to be enrolled in this study. To maximize efficiency and to utilize established systems for screening and follow-up, individuals who themselves are HIV-1 negative, but who have recently infected partners will be recruited from the ongoing 034 HPTN trial. Enrollment will be offered to all participants in HPTN protocols who fulfill the enrollment inclusion/exclusion criteria. Individuals will necessarily have had a previously documented negative HIV-1 test that will be confirmed by HIV-1 RNA PCR. Appendix A (Table 1) reflects the clinical and laboratory specimens that will be collected at each visit. In this protocol, only samples from exposed-uninfected individuals will be collected. Samples from seropositive and seronegative individuals enrolled in the 034AHPTN Early HIV-1 Infection Study Laboroatory Sub-study will serve as comparative controls for the assays performed in the exposed-uninfected study.

3.0 Study Population:

3.1 Inclusion Criteria for HEPS Subjects

Eligible subjects would include individuals from the following population:

• HIV-1 uninfected partners of those enrolled in the 034A HPTN Early HIV-1 Infection Laboratory Sub-study.

All of the following must be fulfilled:

- Willing and able to provide informed consent
- \bullet > 18 years of age
- Willing to permit phlebotomy of four tubes of blood every three months for 24 months

3.2 Exclusion Criteria

- An obvious psychological/psychiatric disorder that would invalidate the informed consent process or otherwise contraindicates participation in the study.
- ♦ HIV-1 infected
- ◆ Hemoglobin level < 7mgs/dl

3.3 Conditions for Participant Withdrawal

A participant may be discontinued early from the study for any of the following reasons:

- Participant withdraws consent/decides that s/he does not want to continue in the study.
- A clinician or the site PI decides that continued participation is not warranted or advisable due to health reasons or other reasons related to the well-being of the participant, including an obvious psychological/psychiatric disorder that would invalidate the informed consent process, or otherwise contraindicate participation in the study.
- Any other condition that in the opinion of the study site Principal Investigator will interfere with achieving the study objectives. The decision to withdraw the participant should be done in consultation with the Protocol Co-Chairs and HPTU Core Protocol Team.

Reasons for discontinuation from the study will be recorded on the appropriate case report form.

4.0 STUDY PROCEDURES

This section refers to laboratory procedures that will be used to evaluate outcomes for each of the primary objectives. The following procedures will be used to accomplish the primary objectives listed below.

4.1 Screening and Enrollment

Individuals who are identified as the sexual partner of participants enrolled in the 034 HPTN Early HIV-1 Infection Laboratory Sub-study will be eligible for enrollment in this protocol. Participants in the Early HIV-1 Infection study will be asked to provide consent to inform their partners of their recent HIV-1 infection. The partners who are then referred to the HPTU clinics for HIV-1 screening, by the participants in the HPTN Early HIV-1 Infection study, will be provided counseling and offered HIV-1 screening testing according to procedures at the NARI site, following informed consent. These exposed partners of recently HIV-1 infected individuals will be subsequently defined as either A) HIV-1 antibody positive, B) recently HIV-1 infected or C) HIV-1 -exposed, but uninfected (laboratory definitions of these three categories provided below). HIV-1 -antibody positive partners of recently HIV-1 infected subjects will be counseled and referred to care and support services available. Recently HIV-1 infected partners of recently infected subjects would themselves be eligible for enrollment in the companion HPTN Early HIV-1 Infection Study. HIV-1 -exposed, but uninfected partners of HIV-1 infected partners in the HPTN Early HIV-1 Infection Study would be eligible for enrollment in this HPTN protocol.

The schedule of visits and procedures is presented in Appendix A (Table 1). At enrollment, informed consent will be obtained and participants will be counseled appropriately for their HIV-1 status. Eligibility will be confirmed and locator information will be obtained. Demographic information will be obtained. A physical exam will be completed. If symptoms of a sexually transmitted disease are present at enrollment or during follow-up, diagnosis and referral for treatment will be provided as locally appropriate. Specimens will be collected, processed and stored or shipped according to the protocols outlined in the site-specific study manual. The next appointment will be scheduled and the appropriate data collection forms will be completed.

To maximize efficiency, established systems for screening and follow-up at each site will be utilized to the extent possible, including the use of home visitors, modest incentives, and tracking procedures. If a participant misses a scheduled study visit, the study site staff will try to establish communication with the participant through all possible means using the contact information provided by the volunteer. The need to adhere to the visit schedule will be emphasized at each contact. Participants may be compensated for meals, time away from work and for transportation to the study clinic as appropriate on a site-by-site basis.

At all visits (enrollment and follow-up) whole anticoagulated blood will be obtained using four 10 ml purple-top EDTA tubes. Blood should be processed within 12 hours of collection. NARI will follow specific protocols for processing and storage of PBMC and plasma.

Individuals with acute HIV-1 infection are highly infectious to their sexual contacts and with whom they may share needles. The ethical concerns surrounding this issue are important,

complex and will require comprehensive review and discussion. Of particular importance are the ethical issues concerning contact tracing, protecting the confidentiality and human rights of the participants and their sexual contact, as well as access to the best available local care for HIV-1 infection. These issues are important for all HIV-1 prevention studies for which HIV-1 infection (i.e. HIV-1 antibody seroconversion) is the primary or secondary endpoint. However, they are particularly important in the setting of acute HIV-1 infection, due to the increased risk of secondary transmission. Participants enrolled in this study will be eligible because of their exposure to partners with acute HIV-1 infection. Thus they will be strongly counseled to reduce their risk of subsequent sexual and needle exposure. It is therefore critical that the Pune site is committed to providing the best available risk reduction counseling for study participants throughout their participation in this protocol. If counseling of participants in this protocol is 100% effective, then none of the participants would subsequently be exposed to HIV-1 infection. Although this should be the goal of counseling for all of the study participants, this protocol is proposed with the recognition that a 100% reduction of risk is unlikely.

4.2 Follow-up

At each follow-up visit, the participant's identity and ID number will be verified. A physical exam and questionnaire will be completed. Specimens will be collected, processed and stored/shipped according the study-specific procedures manual (Appendix A). The next appointment will be scheduled (if required) and the appropriate data collection forms will be completed.

4.3 Laboratory Procedures

The laboratory procedures for this protocol are similar to what is proposed for the companion HPTN Early HIV-1 Infection Protocol. The training, technology transfer and quality control activities for these two protocols will be coordinated by the HCL.

4.3.1 Diagnosis of HIV-1 Infection:

NARI will utilize their own site-specific criteria for identifying individuals with HIV-1 infection. NARI will utilize commercially available HIV-1 antibody assay kits for HIV-1 screening. To be documented as HIV-1 antibody positive for the purposes of this protocol, eligible subjects must have a current positive HIV-1 antibody test and a negative HIV-1 antibody test result within the prior 6 months. A positive antibody test would be defined as either A) HIV-1 + by two different rapid tests B) HIV+ by two different serum ELISA tests C) HIV+ by one rapid AND one serum ELISA test or D) HIV+ by either a rapid test OR an ELISA AND by one HIV-1 western blot. As outlined above, individuals who are NOT HIV-1 antibody positive, based upon any of the above four criteria, will be eligible for enrollment in this protocol. In addition to identification of recent antibody seroconvertors, sites may utilize their own procedures for screening antibody negative specimens using either commercially available HIV-1 p24 Ag assays or HIV-1 PCR assays (see below) to determine eligibility for participation in this protocol.

4.3.2 HIV-1 PCR and Viral Load Testing:

The Pune site will be expected to perform HIV-1 PCR and viral load (VL) measurements for studies outlined in this protocol, as well as other potential HPTN protocols such as preparedness studies, perinatal studies, and ART protocols requiring VL measurements. The HCL will recommend the use of the Roche Amplicor HIV-1 Monitor[™] Test version 1.5 because of its increased sensitivity and ability to detect non Clade B subtypes of HIV-1 (38). This assay would be recommended for sites interested in screening HIV-1 antibody negative specimens for identification of HIV-1 PCR+ subjects in the "window" period for enrollment in the companion HPTN Early HIV-1 Infection Study. This same assay would be utilized on-site for all VL assays for study participants. The HCL virology core will provide training for this HIV-1 PCR assay. This assay contains quality control material in the form of negative, low and high standards that will be used with each assay run. There is also an internal standard control that is assayed with each specimen. Sites will also be required to participate in QA proficiency testing on a quarterly or semi-annual basis through a DAIDS-sponsored Virology Quality Assurance (VQA) program already in place in the US. More detailed information on the viral load assay is provided in Appendix B.

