5.0 Evaluation of Outcomes

5.1 Primary Outcomes

Following the successful implementation of immunologic (ELISPOT) and virologic (viral load measurements) assays at NARI (See quality control and training details above), this project will collect data to address the two stated primary objectives.

5.1.1.Primary Objectives (a).

To determine if the detection of an HIV-1 -specific immune response in exposed uninfected individuals, correlates with risk of subsequent HIV-1 infection.

The initial research hypothesis for this objective, based upon a few prior studies of HIV-1 exposed, uninfected individuals, is that exposed uninfected individuals with CD8mediated recognition of HIV-1 -gag epitopes will demonstrate a lower risk of subsequent HIV-1 infection, compared with exposed individuals that do not recognize HIV-1 gag epitopes. A further hypothesis is that this correlation will be demonstrated in exposed uninfected individuals, who are exposed to recently infected individuals infected with different strains of HIV-1. The primary outcome measures for this analysis will be subsequent HIV-1 infection within the first 2 years of follow-up, and demonstration of an HIV-1 gag-specific response measured in an ELISPOT assay. Based upon this initial analysis of gag-responses and upon data from other ongoing studies, we propose to consider expanding this ELISPOT analysis to include assessment of recognition of other HIV-1 antigens, including env, nef and tat.

5.1.2. Primary Objectives (b).

To determine if immunologic genetic characteristics of exposed uninfected individuals correlates with risk of subsequent HIV-1 infection, across diverse populations.

The initial research hypothesis for this objective, based upon prior studies in a few countries demonstrating that certain HLA class I alleles may be associated with a lower risk of HIV-1 infection, is that there are specific host genetic characteristics that will be associated with a lower risk of HIV-1 infection in exposed individuals from diverse populations infected with different strains of HIV-1. The primary outcome measure for this analysis will be subsequent HIV-1 infection, defined as above, and HLA class I allelic genotype. Based upon this initial analysis of the HIV-1 class I alleles and upon data from other ongoing studies, we propose to consider expanding this analysis to include assessment of HLA Class II alleles and co-receptor genotyping.

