5.1.3 Primary Endpoints

- (a) HIV-1 antibody seroconversion
- (b) ELISPOT measurement of HIV-1 peptide-specific T lymphocytes
- (c) HLA-Class I MHC alleles

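### 034B section 4.3.1 defines HIV-1 antibody positive by 034A's six-month recent-infection rule, which conflicts with 034B's own test criteria, partner categories and primary endpoint

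*Supplement*

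**What the plan says.** 034B section 4.3.1 introduces its definition with "To be documented as HIV-1 antibody positive for the purposes of this protocol" and then requires that "eligible subjects must have a current positive HIV-1 antibody test and a negative HIV-1 antibody test result within the prior 6 months". It goes on to list four test combinations, A to D, that make an antibody test positive.

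Other 034B text bears on the same status:

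- Section 4.3.1, opening: "NARI will utilize their own site-specific criteria for identifying individuals with HIV-1 infection".
- Section 4.3.1, after the four criteria: "individuals who are NOT HIV-1 antibody positive, based upon any of the above four criteria, will be eligible for enrollment in this protocol".
- Section 3.2: being HIV-1 infected is an exclusion.
- Section 4.1: referred partners are sorted as "either A) HIV-1 antibody positive, B) recently HIV-1 infected or C) HIV-1 -exposed, but uninfected (laboratory definitions of these three categories provided below"). The first group is counselled and referred, the second may enter 034A, and the third may enter 034B.
- Section 5.1.1: the primary outcome is "subsequent HIV-1 infection within the first 2 years of follow-up".
- Section 5.1.3: the first primary endpoint is "a) HIV-1 antibody seroconversion", with no interval attached.
- Section 6.3: participants are divided into infected and uninfected, and the two groups are compared on any prior ELISPOT response.

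Section 4.4.1 of 034A contains nearly the same six-month sentence. There it serves a study that enrols people with recent infection.

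**The concern.** A rule that identifies recent infection does a different job from a rule that identifies infection. 034B needs the second for its endpoint and needs both, kept apart, for sorting partners. Only the first is written down, and it carries the name of the second.

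Two things are at stake. First, infection status defines the groups compared in both primary analyses (ELISPOT response and HLA alleles). If the written definition is applied to follow-up tests, someone who seroconverts after a long gap has no defined status: the text does not say whether that person is infected, uninfected or censored. The people affected are those who miss or delay visits, so the ambiguity may not fall at random. Second, site staff sorting partners under section 4.1 have no definition that fits a partner with long-standing infection.

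**Working it through.** **Step 1: passages side by side.** Take a partner who is positive on criteria A-D and has no negative test in the past six months.

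| 034B text | Result for this partner |
|---|---|
| 4.3.1 definition (positive now, negative within six months) | Not documented as antibody positive |
| 4.3.1 eligibility sentence (criteria A-D only) | Antibody positive, not eligible |
| 4.1 category A, using the 4.3.1 definition | Does not fit |
| 4.1 category B, recently infected | Does not fit by the six-month route |
| 4.1 category C, exposed-uninfected | Does not fit; positive on A-D |
| 3.2 exclusion | Excluded as HIV-1 infected |

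The first two rows contradict each other within one section. The three categories leave this partner out, whereas 034A section 4.2 has a class for chronic infection of unknown duration. The definition also asks eligible subjects to have a positive test, in a sub-study that excludes infected people. That is a sign the sentence was carried over.

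**Step 2: the endpoint.** Take a participant who is negative at month 3, absent at months 6 and 9, and positive at month 12. The gap is 12 - 3 = 9 months. Sections 5.1.1 and 5.1.3 describe this as an event. Section 4.3.1 does not allow it to be documented as antibody positive.

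**Step 3: how often this could arise.** The plan gives no figure to reproduce and no missed-visit rate, so this is an illustration. From the documents: an HIV test at each three-monthly visit (034B Appendix A, Table 1) and a two-year outcome window, hence 8 follow-up tests. Assumed: infection time uniform over 24 months, and each visit missed independently with probability *m*.

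The gap is 3 × (consecutive missed visits + 1) months: 3 with none missed, 6 with one, 9 with two. Averaging over the eight intervals:

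- P(detected) = 1 - (m + m² + … + m⁸)/8
- P(detected, gap 3 months) = [(1-m) + 7(1-m)²]/8
- P(detected, gap 6 months) = [2m(1-m) + 12m(1-m)²]/8
- Share with gap strictly over 6 months = 1 - (second + third)/first

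At m = 0.10: detected 0.98611; gap 3 months (0.9 + 5.67)/8 = 0.82125; gap 6 months (0.18 + 0.972)/8 = 0.144. The share over six months is (0.98611 - 0.82125 - 0.144)/0.98611 = 2.1%.

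| Assumed m | Gap strictly over 6 months | Gap 6 months or more |
|---|---|---|
| 5% | 0.55% | 8.6% |
| 10% | 2.1% | 16.7% |
| 19% | 7.2% | 30.4% |

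A simulation of the same model agrees to within 0.1 percentage point. The right-hand column is an upper limit. It adds every gap made by one missed visit, and such a gap breaches six months only if the participant then returns late. The parent protocol's revised Clarification Memo #1 accepts visits within 22 days of schedule, so some late returns are to be expected.

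**Step 4: in events.** The stated minimum of 20 participants and the assumed 20% seroconversion (034B section 6.3) give 20 × 0.20 = 4 events. Expected events with a gap strictly over six months: 4 × 0.0055 = 0.02 to 4 × 0.072 = 0.3.

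**The case against.** The strongest reply is that the endpoint is sound as written. Neither 5.1.1 nor 5.1.3 sets an interval limit, no endpoint or analysis passage cites 4.3.1, and the disputed sentence speaks of eligible subjects, which is entry language. The section also opens by leaving identification of infection to the site's own criteria. A reader might infer that the plan removes late-detected infections from the primary endpoint or counts them as uninfected. The documents do not say so, and that inference should not be drawn. What remains is that the only written definition of documented positivity in 034B conflicts with its endpoint, and the site-criteria sentence supplies no definition to settle the matter.

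A reader might also infer that chronically infected partners could be enrolled. They could not: the section 3.2 exclusion and criteria A-D both bar them. The defect there is one of classification and touches no analysis set. Nor is recent infection identical to the six-month rule, because 034A section 3.1 also admits people by detuned ELISA, or by PCR or p24 antigen when antibody is negative or indeterminate.

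Finally, the size is modest. The main protocol's 90% and 81% semiannual retention figures are not missed-visit rates, and someone lost for good never returns with a positive test for this rule to reject. The earlier acute-infection cohort kept 33 of 35 (94%) over 24 months, and 034B section 4.1 provides for contacting participants who miss visits. One lost event would be a quarter of four, but that is the weight of one event and not the expected loss. All of this stands. It limits the consequence without removing the contradiction.

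**Conclusion.** The contradiction is real and can be shown from the text alone. Section 4.3.1 gives 034A's recent-infection rule the name of antibody positive, against its own eligibility sentence, the section 4.1 categories and a two-year outcome without an interval limit. It is a conflict to reconcile, not a stated exclusion from the endpoint.

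On the endpoint the effect is small if attendance is good: roughly half a per cent to 7% of detected infections under assumed missed-visit rates of 5% to 19%, and more where a single missed visit is followed by a late return. These figures rest on independent misses and uniform infection times, neither of which the documents establish. Misses related to risk could make the effect larger or smaller. With about four events expected at the minimum size, imprecision will outweigh any bias from this source, but each event still needs an unambiguous status. The correction is worth making because it is cheap and concerns the definition of the primary endpoint.

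**What to change.** Amend 034B as follows:

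1. **Section 4.3.1:** define HIV-1 antibody positive by test criteria A-D alone and remove the six-month condition from that definition.
2. **Sections 5.1.1 and 5.1.3:** define the endpoint as the first confirmed A-D positive after a negative enrolment test, whatever the gap, within the two-year window.
3. **Infection date:** state how it is estimated from the last negative and first positive tests. The set-point endpoint (6 to 12 months after estimated infection) and the requirement that an ELISPOT response be prior to infection both depend on it. After a 9-month gap, a midpoint could be wrong by up to 9/2 = 4.5 months in either direction, so also state how such cases enter those two analyses.
4. **Section 4.1:** define recent infection by reference to 034A section 3.1, keeping all its routes (documented seroconversion within six months, detuned ELISA, and PCR or p24 antigen). Put the remaining antibody-positive partners in a class of chronic infection or unknown duration, as 034A section 4.2 does. The categories then do not overlap and none is missing.

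The cost is a few sentences of protocol text and the amendment approvals the sub-study already requires. No extra visits or tests are needed.
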